ImmigrantScreen

“Creating a more equitable breast cancer screening program by approaching immigrant women in a familiar language”

[name], Principal Investigator
[name], Project Leader
[name], Research assistant
[name] student, Research assistant
[name], Research assistant
[name], Research assistant
[name], Research assistant
All at the Cancer Registry of Norway

Date: February 2023

Revision history

Version number	Date
Version 0.1	January 2021
Version 0.2	February 2023

[name]

03022023

Study Leader

[name]

Date

06. 02. 2023

Principal Investigator

Date

Clinical study summary

Title:	ImmigrantScreen - Increasing access to breast cancer screening among immigrants
Study objectives:	Examine whether an invitation to breast screening in the language of origin influenced attendance.
Clinical study design:	Randomized controlled trial.
Inclusion / exclusion criteria:	
Inclusion criteria: Female sex, screening age, birth country of Algeria, Egypt, Iraq, Lebanon, Morocco, Palestine, Pakistan, the Philippines, Poland, Somalia, Sudan, Syria, or Tunisia, representing the following languages: Arabic, English, Polish, Somali and Urdu.
 
Exclusion criteria: Diagnosed breast cancer before invitation, missing information about birth country.

Primary performance endpoints:	Attendance
Secondary performance endpoints:	Attendance after primary invitation, attendance after a reminder, stratified by age and country of birth.
Safety endpoints:	Breach of privacy or a significant drop in attendance.
Duration of study:	Approximately one year for recruiting women and two years for running analyses and publications
Follow-up:	Not applicable

Table of Contents

Clinical study summary.....	2
Table of Contents	3
1 Introduction.....	4
2 Study Description	4
2.1 Background.....	4
2.2 Study Rationale.....	5
3 Objectives and hypothesis	6
3.1 Objectives	6
3.2 Hypothesis	6
3.4 Risks and anticipated adverse events that are to be assessed.....	6
4 Project methodology.....	7
5 Study design	7
5.1 General	7
5.2 Study intervention	8
6 Risks and benefits.....	8
6.1 Anticipated benefits.....	8
6.2 Anticipated risks	8
6.3 Data and Safety Monitoring Board.....	9
7 Statistical considerations.....	9
7.1 Statistical design	9
7.2 Trial participants and expected attendance	9
7.4 Variables of interest.....	11
7.5 Provision for interim analyses	11
7.6 Criteria for terminating the clinical study.....	11
7.7 Specification of subgroups.....	11
7.8 Treatment of missing, unused, spurious data	11
8 Data management.....	11
9 Amendments to the research protocol.....	12
10 Deviations from the research protocol	12
11 Statements of compliance.....	12
12 Informed consent process.....	12
13 Suspension or premature termination of the clinical study.....	12
14 Publication policy	13
15 Bibliography.....	13
Appendix – invitation letter and leaflet.....	15

1 Introduction

This two-armed, parallel group, blinded, pragmatic randomised controlled trial is designed to examine the potential superior effect on attendance when inviting immigrant women targeted BreastScreen Norway to mammographic screening in their presumed language of origin and in Norwegian versus in Norwegian only. The study is aimed at enrolling 14,000 immigrant women.

Breast cancer is the most common cancer among women in Norway and word-wide (1). In Norway, almost 3700 women were diagnosed with breast cancer and 600 died from the disease in 2017 (2). The national screening program for breast cancer, BreastScreen Norway, started in 1996 (3). The primary goal of the screening program is to reduce breast cancer mortality through early detection. The annual attendance rate in the program is about 75%, however immigrant women have a substantially lower attendance rate compared to non-immigrant women (4). A qualitative study have highlighted some of the barriers for immigrants to attend screening, among those were the invitation letter and language (5).

BreastScreen Norway and the Norwegian colorectal cancer screening program joined forces and applied for funding to investigate whether invitations to screening in a major language in invited immigrant's country of birth would increase attendance. The application successfully asked for funding for three studies: a randomized controlled trial (RCT) of inviting women to BreastScreen Norway in their language of origin, a similar RCT for the colorectal cancer screening program, and a qualitative study.

This protocol covers the first of the three studies proposed, in which we will perform an RCT to investigate whether receiving a translated version of the invitation letter and information leaflet ("invitation letter") in the official language of the country of birth ("official language") increases the attendance rate of immigrant women invited to BreastScreen Norway.

2 Study Description

2.1 Background

2.1.1 Breast cancer incidence, risk and survival

Breast cancer is the most common cancer among women in the world and in Norway (1). The lifetime risk of the disease is 8% and 5-years relative survival is 90% (2). Breast cancer mortality has decreased during the last decades and Norway has the lowest rates among all Nordic countries (6). Implementation of high-quality screening for women aged 50-69 years, and improved treatment are the reasons for this improvement (7).

2.1.2 Breast cancer in immigrant population groups in Norway

Today, 14% of the Norwegian population are immigrants, defined as residents of Norway having been born outside of Norway by two parents born outside of Norway (8). The Norwegian immigrant population is heterogeneous, due to the large variation in countries of origin as well as reasons for immigration. Breast cancer incidences vary widely between immigrant groups, reflecting the incidence in the countries of origin (9). The age-standardized breast cancer incidence is slightly higher in immigrants from Northern and Western Europe compared to non-immigrants, and lower in immigrants from Asia and Sub-Saharan Africa.

2.1.3 BreastScreen Norway

BreastScreen Norway invites all women aged 50-69 to two-view mammographic screening every two years (10). The aim of the screening program is to detect breast cancer in an early stage and thereby reduce the

treatment burden and mortality from the disease. The women are offered screening through a personal invitation letter in Norwegian (regular mail or digital mailbox), with stated time and place for the examination. Screening takes place at 30 mobile or stationary units distributed around the country. A reminder is sent to non-attending women 4–6 weeks after the originally scheduled appointment, offering the women an opportunity to schedule a new appointment by contacting the local breast center. Three in four women attend each screening round. Further assessment takes place at 17 breast centers, centrally located and distributed across all counties. About 3% of the women are recalled from screening for further assessment, while about 20% of the recalled women are diagnosed with breast cancer. The effects of mammographic screening, mainly on the reduction of breast cancer mortality and on overdiagnosis, have been discussed during the last decades. The International Agency for Research on Cancer (IARC) and other health authorities including the European Commission Initiative on Breast Cancer (ECIBC) consider the benefits to outweigh the harms and mammographic screening is offered to women in all continents (11-13).

2.1.4 Inequalities in cancer screening

Demographic characteristics are shown to vary between attendees and non-attendees in breast cancer screening (14). However, for colorectal cancer, contextual elements such as demographic characteristics and offered screening method differ between countries (15). Therefore, reasons for non-attendance may depend on factors such as region of origin. Poor adherence to screening recommendations among immigrants has been shown for breast and cervical cancer screening in Norway (4, 16). The uptake also varies between different immigrant and ethnic groups. A qualitative study from BreastScreen Norway identified several mediating factors of influence for attendance in a group of immigrants, such as examiner's gender, invitation letters, relatives, and religion (5).

2.1.5 Data on country of origin in the Cancer Registry of Norway

As a result of recent studies showing differences in breast cancer screening uptake between immigrant groups (4, 17), data from Statistics Norway about country of origin for immigrant citizens is now available in the Cancer Registry of Norway without consent from the individual. Further, country of origin is available to screening program planners, enabling language-targeted information. This gives a unique opportunity to study the effect of information about cancer screening given in the presumed maternal language of immigrant groups. In most parts of the world, cancer screening uptake is lower in socio-economically deprived groups, and in immigrants than the rest of the population (18, 19). A recent publication from BreastScreen Norway showed a substantially lower attendance rate among immigrants compared to non-immigrants, 56% versus 78% (4). Among Somali women, only 14% attended BreastScreen Norway. Similar findings are shown for cervical cancer screening (16).

2.2 Study Rationale

The prerequisite for an effective cancer screening program is acceptance of the invitation. A goal is equally accessible cancer screening program to all women in the target group. According to the so-called Nordic welfare model, the entire population should have equal access to health care (20). This means that the discrepancy in attendance in screening between women born in Norway and women born abroad by foreign-born parents reduces the equity of the screening program. There are several barriers to attending breast cancer screening, and these can vary according to people's background. One known barrier to cancer screening is the lack of awareness and understanding of the screening invitation, which compromises the invitee's ability to make an informed choice about attending (21, 22). In BreastScreen Norway, the invitation letter and information leaflet are in Norwegian only. The most essential information is available in English on

the webpage of Cancer Registry of Norway. Lack of information in different languages might be of influence for the attendance rate (22). Ideally, all invitees to cancer screening should be offered information in a way which allows them to make an informed choice whether to attend or not. To ensure that invitation to cancer screening is an equitable health service for all, action should be taken to make sure that the invitation letter is understood by all invitees.

Sending invitation letters to screening in the official language of selected immigrants birth countries may signal to these immigrant resident groups that the health authorities care for them and are striving to reach them. Yet, the effect of sending invitations in immigrants presumed maternal language has not been investigated in Norway, and there is currently a lack of knowledge on how to increase attendance in BreastScreen Norway among immigrants. Most studies have been conducted outside Europe and the needs and type of information are constantly changing. A recent Norwegian trial has tested how to increase cervical screening uptake in immigrant women (23).

To advise the Norwegian health authorities about how to reach groups in need of adapted information on breast cancer screening and to contribute to fill knowledge gaps related to mammographic screening for immigrants, we will test the effect of translated information when inviting immigrant residents in Norway to BreastScreen Norway in their language of origin by conducting an RCT, comparing the attendance among immigrant receiving the invitation letter and the information leaflet in the presumed language of origin and Norwegian, versus Norwegian only.

3 Objectives and hypothesis

3.1 Objectives

3.1.1 Primary objective

To study the effect on attendance of inviting selected immigrant groups to BreastScreen Norway by translated invitation letter and information leaflet in the major official language of the woman's country of birth, in addition to Norwegian, versus in Norwegian only.

3.1.2 Secondary objective

To study whether the effect on attendance of inviting selected immigrant groups to BreastScreen Norway by translated invitation letters in the major official language of the woman's country of birth differs across country of birth – five language groups with a substantial number of women in the target group of the screening program will be selected. We will also stratify the outcome by age, screening history and residential time in Norway.

3.1.3 Other study objectives

We will study recall rates, cancer detection and characteristics of the tumor.

3.2 Hypothesis

We expect that immigrant women in the intervention group (major official language and Norwegian) will have a higher attendance rate compared to the control group (Norwegian only).

3.4 Risks and anticipated adverse events that are to be assessed

The risk of this study is that an invitation in the major official native language of the women's country of birth will lead to lower attendance.

4 Project methodology

We will run a randomized clinical trial (RCT) in five language groups, sending an invitation letter in a major official language in addition to Norwegian to a randomly assigned half of the women, while the other half will receive an invitation only in Norwegian according to normal procedures (randomization 1:1 within each language group). Attendance rates, attendance among the invited, in the two arms will be compared. Based on results of 2018 the study by Bhargava et al. we will include women born in Poland, the Philippines, Pakistan, Somalia, and Arabic speaking countries (Iraq, Syria, Lebanon and Palestine) (4). These women have a low attendance rate in BreastScreen Norway and the number of women in the target group is sufficient to detect a difference in attendance (see chapter 7.4 for minimal effect size detectable). Descendants of immigrants will not be included in the RCT. All information material, including the invitation letter, information leaflet, response letter, and invitation reminder, will be translated by a professional agency, quality assured by professionals and tested by health professionals and women in the target group. The translation work started in January 2020, while a pilot of the trial will be performed during the fall 2020. The RCT will start January 2021 and run for one year. Quality assurance will run throughout 2021. Results will be analysed, interpreted, and disseminated during 2023.

5 Study design

5.1 General

5.1.1 Description

We will perform a *randomized controlled trial*. The study has *two arms* to which women can be randomized – an intervention arm and a control arm. The intervention arm consists of five different *strata*: the Arabic stratum, the Filipino stratum, the Pakistani stratum, the Polish stratum, and the Somali stratum. As the randomization in this study is stratified, women are first divided into strata, and then randomly assigned to either the intervention or the control arm. The study has a *parallel group design*, meaning there are no crossovers between the two arms. The intervention arm will only get the intervention, and the control arm will never receive the intervention. As the study is *blinded*, women are de-identified before they are randomized and will remain pseudonymized to the researchers throughout the study period. The study is *pragmatic*, meaning it will be embedded within BreastScreen Norway, and data collection will take place in an everyday screening setting. In summary, this is a two-armed, parallel group, blinded and pragmatic randomized controlled trial.

5.1.2 Primary endpoint

The primary endpoint of this study is **attendance**, defined as the number of women attending a screening examination among the number of women invited to a screening examination during the study period. The study will compare attendance in the two groups.

5.1.3 Equipment, databases and systems

The equipment needed to perform this trial is the data system at the Cancer Registry of Norway with which the target population is defined, invited, and recorded in BreastScreen Norway. With this system, administrative employees from the Cancer Registry of Norway selects cohorts and groups of women to invite based on their place of residence in a standard setting. Women targeted by the screening program are identified through the National Population Register. The data system then automatically selects women with the longest time interval since the previous invitation. When women are selected, an invitation

number and an invitation is generated in the **invitation table**, with an automatically generated appointment. The invitation is sent in the form of a letter (physical or digital depending on the woman's preference for governmental communication), together with an information leaflet designed to guide the women to make an informed decision on whether to attend or not.

For this RCT, a **study table** will be created in the database of BreastScreen Norway. Whenever a woman is to be invited, the invitation system will check whether her personal identification number exists in the study table, and if it does, checks whether she is registered with a 0/1 for control/intervention group and what language she is to be invited in if in the intervention group (1 for Somali, 2 for Polish, 3 for English, 4 for Urdu, 5 for Arabic). When the women attend at the screening unit, they are interviewed, and imaged ("examination" hereafter) by radiographers. When the radiographer's registers data from this examination in a software connected to the database at the Cancer Registry of Norway, it is stored in the **attendance table**. Women are registered in the databases with a personal identification number, which makes it possible to merge all these tables into study tables for different projects.

5.2 Study intervention

5.2.1 Description

The intervention in this study is defined as sending a **physical invitation letter and an information leaflet (2 items) in the women's language of origin and Norwegian**. A physical reminder and a physical response letter are sent in the women's language of origin and in Norwegian. The language in the translated versions follows the strata and are as follows: Arabic in the Arabic stratum, English in the Filipino stratum, Polish in the Polish stratum, Somali in the Somali stratum, and Urdu in the Pakistani stratum. The translated versions of the letters are found in the appendix. The Arabic stratum includes women born in Algeria, Egypt, Iraq, Lebanon, Morocco, Palestine, Sudan, Syria, and Tunisia.

5.2.2 Comparator

The **comparator** in this study is defined as sending a **physical invitation letter and an information leaflet (2 items) in Norwegian**. A physical reminder and a physical response letter are sent in Norwegian. The comparator is the current standard of practice in BreastScreen Norway.

6 Risks and benefits

This study is not a clinical study, and as such, there no major expected risks to the participants. A risk analysis is therefore not performed.

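### Does calling a paper letter current practice, when routine invitations may be paper or digital, undermine the comparison of the two arms?

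*Protocol*

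**What the plan says.** Section 5.2.1 defines the intervention as a "physical invitation letter and an information leaflet (2 items) in the" woman's language of origin together with Norwegian, and makes the reminder and response letter physical too. Section 5.2.2 defines the comparator in parallel terms: a "physical invitation letter and an information leaflet (2 items) in Norwegian", followed by "A physical reminder and a physical response letter are sent in Norwegian". It closes with "The comparator is the current standard of practice in BreastScreen Norway".

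Three other places bear on this.

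- Section 2.1.3, in the background, says women are offered screening through a "personal invitation letter in Norwegian (regular mail or digital mailbox", which closes the parenthesis on two channels.
- Section 5.1.3, describing the invitation system, says the invitation is "sent in the form of a letter (physical or digital depending on the" preference each woman has registered for official mail.
- Section 4 says the control half "will receive an invitation only in Norwegian according to normal procedures".

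On language, section 2.2 is clear about existing practice: "the invitation letter and information leaflet are in Norwegian only".

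**The concern.** Take a woman who prefers digital mail and is randomised to control. Section 5.2.2 gives her paper. If section 4 is read together with the routine rule in section 5.1.3, she gets a digital letter. Both cannot be true of her, and section 5.2.2 calls the paper version current practice.

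Two things could be at stake.

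- **Validity.** If controls followed the routine channel while every intervention woman received paper, women who prefer digital mail would receive paper in one arm only. The attendance difference would then mix the effect of language with the effect of channel, whereas the primary objective (3.1.1) concerns language alone.
- **Use of the result.** The trial is called pragmatic (5.1.1) and is meant to inform the health authorities (2.2). A reader who trusts the label would take the control arm for usual care in every respect, including its mix of paper and digital mail.

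The trial-specific text does not visibly rule out the first possibility. The study table in 5.1.3 is described as holding arm and language, section 8 speaks only of inviting each participant in the right language, and channel is not among the background variables in 7.4.

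**Working it through.** The protocol states no figure on this point, so the check is mainly a comparison of texts.

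**1. Which statements are trial rules?**

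| Section | Subject | Channel stated | Status |
|---|---|---|---|
| 2.1.3 | Screening programme | Paper or digital, invitation letter | Background |
| 5.1.3, first paragraph | Routine invitation system | Paper or digital by preference, invitation letter | Description of standard operation |
| 5.1.3, second paragraph | Study table for this trial | None; arm and language only | Trial-specific |
| 4 | Control half | None; refers to normal procedures | Trial overview, contrasting languages |
| 5.2.1 | Intervention arm | Physical letter, reminder, response letter | Operative definition |
| 5.2.2 | Control arm | Physical letter, reminder, response letter | Operative definition |

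The only two sections that define what each arm is sent agree with each other. Each uses the word physical three times, for the same three mailings. A single channel rule for both arms is therefore already stated.

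**2. Does section 4 override it?** The sentence sets a letter in a major official language plus Norwegian against one in Norwegian only. The reference to normal procedures completes that contrast. Read with section 2.2, it says that controls get the existing Norwegian text. It names no channel.

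**3. How far does the contradiction reach?** Less far than it first appears. Only 5.1.3 ties the channel to preference; 2.1.3 merely lists two channels. Both speak of the invitation letter. Section 2.1.3 mentions the reminder but gives no channel for it, and no section gives a routine channel for the response letter. Nothing shows that a physical reminder or response letter departs from standard practice. The mismatch is limited to one label applied to one mailing.

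**4. What would a channel difference do?** Let f be the share of controls sent a digital letter while their intervention counterparts get paper, and let c be the effect of channel on attendance in percentage points. With no language effect, the arms would differ by f × c.

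- Under the definitions in 5.2.1 and 5.2.2, f = 0, so f × c = 0 whatever c is.
- Under the other reading, neither f nor c is in the documents. With assumed values only: 0.25 × 2 = 0.5 points; 0.50 × 5 = 2.5 points; 0.75 × 10 = 7.5 points. Table 3 gives 3 points as the minimal detectable difference for the total.

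The second line shows why the question was worth asking. It is not evidence of bias, because it requires controls to be sent something other than the comparator that the protocol defines.

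**The case for a change.** The best case for a change is that the comparator's content and label are protocol matters, not something to leave to a SAP, and that here they disagree with the description of routine practice. No sentence says that a digital preference is overridden for trial women. A digital Norwegian letter to a control would be a deviation under 5.2.2 yet routine on one reading of section 4. Section 10 has all deviations reviewed, and section 13 unblinds all data if any woman received a wrong letter, without saying whether a wrong channel counts. The repair is a few words, and because this version is dated February 2023, after the planned 2021 invitations, the sponsor could simply state what was sent.

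Part of this stands. The label is inaccurate on channel, and a careful reader will notice. The deviation point, however, exists only if section 4 is taken as a channel rule, which its wording does not support. The absence of channel from 7.4 carries little weight: it is a feature of delivery and not a background characteristic, section 5.1.3 says the registry tables can be merged, and section 8 refers to a data management plan that is not shown. What was actually sent belongs in the trial report, where it can be stated without amending the plan.

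The applicability point is fair but small. Section 5.1.1 explains pragmatic as being embedded in the programme with data collected in ordinary screening. It does not promise the routine mix of channels. Using paper in both arms is a reasonable way to isolate language, at the cost of saying less about women who would normally be reached digitally.

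**Conclusion.** No change to the plan follows. There is a real slip: "The comparator is the current standard of practice in BreastScreen Norway" is true of the Norwegian text and not fully true of the channel. The definitions that govern the two arms nevertheless agree, so the language comparison in 3.1.1 is valid as planned and this source contributes zero bias to it. Rewording the label would leave the randomisation, endpoint, analysis and sample size as they are.

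The conclusion rests on two assumptions: that 5.2.1 and 5.2.2 take precedence over the descriptions of routine operation, and that invitations were sent accordingly. If the trial's records showed that channel differed between the arms, the result would have to be described as the effect of language and channel together. That would be a finding about conduct, and the documents contain no sign of it.
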